6.4.1.1 Future Research

No additional analysis is planned to be performed on the blood samples for possible future research.

6.4.2 Subjective Effects Questionnaires

The Intent to Use (VAS), Urge to Smoke (VAS), and Product Evaluation Scale (7-point scale) questionnaires will be completed using a computerised tablet device and using Veeva ePro. All relevant software and staff training specific to the electronic questionnaires will be provided by Celerion. Any electronic device used must meet all regulatory requirements, including FDA 21 CFR Part 11.

All questionnaires will be completed at the time points delineated in the Study Events Flow Chart ([Table 1](#)).

When scheduled at the same time as a PK blood draw, subjective effects questionnaires will be completed within a timeframe of ± 2 minutes relative to the blood draw. The baseline Urge to Smoke questionnaire will be administered approximately 10 minutes prior to the start of the product use session.

6.4.3 Puff Topography

Puff topography will be evaluated over the last 2-hour period during the 4-hour *ad libitum* product use session on Days 1 through 5 as indicated in the Study Events Flow Chart ([Table 1](#)). Following the 4-hour PK blood collection and at the start of their meal, subjects will be allowed to use their assigned study product *ad libitum* for 4 hours. During the last 2 hours of the *ad libitum* session, topography measurements will be taken. The SPA-M device will need to reset at 60 minutes in order to record 2 hours of topography data. Puff parameters will be recorded using SPA-M devices (puff count, puff duration, puff volume, peak puff flow rate, average puff flow rate, inter puff interval) for each product.

The *ad libitum* product use session on Days 1 through 5 will start at approximately the same time each day, with lunch served at the start of the *ad libitum* product use session, at approximately the same time each day. After completion of the *ad libitum* use session (i.e., approximately 8 hours after the start of the morning controlled product use) on Days 1 to 4, subjects will be allowed to smoke their own cigarettes (*ad libitum*) but will abstain from use of any tobacco- or nicotine-containing products for at least 12 hours prior to the start of morning controlled product use session scheduled on the following day.

The topography device will be monitored to ensure the device is actively recording during each session.

Additional details and instructions for puff topography procedures will be provided separately.

Depending on the availability of topography equipment, puff topography may not be performed for some or all assigned subjects.

6.4.4 Safety Assessments

Safety assessments in addition to those below may be obtained as necessary at the discretion of the Investigator. In the case of an early subject withdrawal, discharge safety assessments should be collected to the extent possible.

6.4.4.1 Physical Examination

A standard physical examination assessing the general physical well-being will be performed at Screening. A symptom-driven physical examination will be conducted at other times as deemed appropriate by the Investigator (Table 1).

6.4.4.2 Body Weight, Height, and BMI

Body weight and body height will be measured as delineated in the Study Events Flow Chart (Table 1). BMI will be recorded as kg/m^2 .

6.4.4.3 Electrocardiogram

Single 12-lead ECGs will be performed as outlined in the Study Events Flow Chart (Table 1). ECGs will be taken following resting in the supine position for at least 5 minutes. All ECG tracings will be reviewed by the Investigator or a qualified designee.

6.4.4.4 Vital Signs

Single measurements of vital signs (respiratory rate, HR, BP, and oral temperature) will be performed as outlined in the Study Events Flow Chart (Table 1). Additional vital signs may be taken at any other times, if deemed necessary.

BP and HR measurements will be taken following a rest period of at least 5 minutes in a seated position. Vital signs are to be measured at least 15 minutes after the last tobacco- or nicotine-containing product used.

On Days 1 through 5, vital signs measurements will be taken within 2 hours prior to the start of the morning product use session.

6.4.4.5 Clinical Laboratory

All clinical laboratory tests will be conducted by an accredited laboratory. Values for the clinical laboratory parameters are to be within the laboratory normal ranges or deemed not clinically significant in the opinion of the Investigator. All tests listed below will be performed as delineated in the Study Events Flow Chart (Table 1). Up to approximately 38 mL of blood will be drawn from each subject during the entire study for clinical laboratory tests.

Serum Chemistry¹

- Albumin
- Alkaline phosphatase
- Alanine aminotransferase
- Aspartate aminotransferase
- Bicarbonate
- Blood urea nitrogen
- Creatinine
- Glucose
- Potassium
- Sodium
- Total protein
- Uric acid

Urinalysis²

- Bilirubin
- Blood
- Glucose
- Ketones
- Leukocyte esterase
- Nitrite
- pH
- Protein
- Specific gravity
- Urobilinogen

Additional Tests

- Serology
 - HIV
 - HBsAg
 - HCV
- Serum pregnancy test³
- Serum FSH⁴
- Urine cotinine
- Urine drug screen
 - Amphetamines
 - Cannabinoids
 - Cocaine
 - Opiates
- Urine/breath alcohol

Hematology

- Hematocrit
- Hemoglobin
- Platelet count
- Red blood cell count
- White blood cell count with differential

¹ Serum chemistry tests will be performed after at least an 8-hour fast; however, in case of dropouts or rechecks, subjects may not have fasted for 8 hours prior to the serum chemistry sample being taken. For the samples collected at EOS, an 8-hour fast is not required.

² A microscopic examination for red blood cells, white blood cells, bacteria, and casts will be performed if an abnormality is noted in leukocyte esterase, protein, blood, or nitrite.

³ Human chorionic gonadotropin (females only).

⁴ For postmenopausal females only.

6.4.5 Adverse Events

An AE is any untoward medical occurrence associated with the use of the study product, whether or not considered study product-related. An AE can therefore be any unfavourable and unintended sign (including an abnormal laboratory finding), symptom, or disease temporally associated with the use of a study product, whether or not related to the study product.

6.4.5.1 Monitoring

The subjects will be instructed to inform the Investigator or staff of any AEs and intercurrent illnesses experienced during the study (i.e., from Screening until follow-up). Additionally, a specific inquiry regarding AEs will be conducted prior to each product use and at discharge (or upon early withdrawal). The inquiry will be posed in a non-specific manner using open-ended questions so as not to bias the response (e.g., How are you feeling today?).

A subject who has any clinically significant AE or clinically significant abnormal laboratory test value will be evaluated by the Investigator or other qualified individual and will be treated

and/or followed up until the symptoms or values return to normal or acceptable levels (as appropriate in the opinion of the Investigator), or until the subject is lost to follow-up. Where appropriate, medical tests and examinations will be performed to document resolution of the event(s).

6.4.5.2 Reporting

All AEs occurring during this clinical trial after the subject has received the first study product (i.e., at the Product Trial) must be recorded on the CRF, including the date and time of onset, action taken, outcome (resolved, improved, unchanged, worse, fatal, or unknown/lost to follow-up), duration, relationship to product administration, and severity for each event. AEs will be listed.

Events captured between Screening and the first study product use will be documented as baseline signs and symptoms.

The Investigator will review each event and assess its relationship to product administration as unrelated, unlikely, possibly, probably, or likely.

In addition, each sign or symptom reported will be graded on a 3-point severity scale using mild, moderate, or severe.

6.4.5.3 Serious Adverse Events

A serious adverse event (SAE) is any AE that in the view of either the Investigator (or designee) or Sponsor, results in any of the following outcomes: death, a life threatening AE, inpatient hospitalisation or prolongation of existing hospitalisation, a persistent or significant incapacity or substantial disruption of the ability to conduct normal life functions, or a congenital anomaly/birth defect. Important medical events that may not result in death, be life threatening, or require hospitalisation may be considered serious when, based upon appropriate medical judgment, they may jeopardise the subject and may require medical or surgical intervention to prevent one of the outcomes listed in the above definition.

All SAEs, whether or not considered study-related, must be reported by telephone and by fax or e-mail to the Sponsor within 24 hours of the CRU's learning of the SAE or, at the latest, on the following workday. The Sponsor's representative to contact about this study is provided in the list of study contacts. The Investigator must also inform the EC, in compliance with GCP reporting guidelines, and the site monitor of any SAE.

6.4.5.4 Suspected Unexpected Serious Adverse Reactions

In accordance with the European Clinical Trial Directive (Directive 2001/20/EC), the Sponsor must ensure that the Ethics Committee, the appropriate Competent Authority, and the licensing authority are informed of all suspected "unexpected" serious adverse reactions (SUSARs) within 15 days of the event. All SUSARs leading to death, or which are life-threatening should be reported by the Sponsor to the ethics committee, the appropriate Competent Authority, and the licensing authority within 7 days of the event. The Sponsor should present all SUSARs to the appropriate Competent Authority once a year, or on request. Reporting of relevant events

to ethics committee, the appropriate Competent Authority, and the licensing authority will be delegated by the Sponsor to the CRO (Celerion).

6.4.5.5 Pregnancy

A pregnancy occurring in a female study subject during the study will be documented in the clinical conduct study report to the EC. Pregnancy itself is not an AE. The Investigator or designee will discontinue the pregnant subject from the study and will advise her to seek prenatal care and counselling from her primary care provider. Advice given will be documented in the subject's source document.

The CRU staff will request the pregnant subject to notify the CRU of the outcome of the pregnancy (i.e., birth, loss, or termination). To help ensure this, the CRU staff will follow up with the subject until the end of pregnancy, if in compliance with the CRU's standard operating procedures (SOPs) and with the subject's consent. This request and the subject's response will be documented in the subject's source document.

6.4.5.6 Smoking Cessation Information

At Screening and prior to discharge from the study (or upon early termination), all subjects will be advised that to reduce the health effects of smoking, the best thing to do is to quit, and will be encouraged to contact a qualified medical professional for advice on smoking cessation.

7. DATA ANALYSIS

Data will be handled and processed according to Celerion SOPs, which are written based on the principles of GCP. A brief description of the statistical analysis is included below, detailed methodology for all summary and statistical analyses of the data collected in this trial will be documented in a statistical analysis plan (SAP) prepared by Celerion and agreed upon by the Sponsor. The SAP may modify the plans outlined in the protocol; however, any major modifications of the primary endpoints and/or their analysis will also be reflected in a protocol amendment. If deemed appropriate, additional statistical analyses other than those described in this section may be performed and included in the plan.

7.1 Sample Size Estimation

The sample size chosen for this study was selected without statistical considerations. It has been determined adequate to meet the study objectives. This sample size chosen is comparable to other similar studies in the literature (e.g., Hardie et al., 2022; Phillips-Waller et al., 2021).

7.2 Analysis Populations

7.2.1 Safety Population

The Safety Population will include all subjects who have successfully completed eligibility requirements after checking in to the CRU and used at least one study product.

7.2.2 Outcomes Population

The Outcomes Population is a subset of the safety population and will consist of subjects who used a study product and have evaluable PK, subjective effects, or topography data. This population will be used in the summary and analysis of PK, subjective effects, topography, and product use, and all available data will be included in the summary tables to the extent possible.

7.3 Data Analysis, Summarisation, and Statistical Methods

SAS software (version 9.4 or higher, Cary, North Carolina) will be used for all data presentation and summarisation including summary tables, graphs, and data listings. In general, all data will be listed by subject and time point and summarised by study product, time point, product use session (as applicable), and sex using descriptive statistics appropriate for the endpoint. Figures will be used to display the data graphically.

Missing data will not be imputed. Where individual data points are missing because of dropouts or other reasons, the data will be considered missing at random and summarised based on reduced denominators.

7.3.1 Nicotine Pharmacokinetic Analysis

Individual nicotine concentrations will be adjusted for baseline nicotine (“baseline-adjusted”) and all PK parameters will be calculated based on the adjusted concentrations. Baseline adjustment will be performed by subtraction of the pre-existing nicotine concentration from each nicotine concentration obtained after test product administration in that period/day for each subject using the following equation:

$$C_t = C_{t \text{ unadjusted}} - [C_0 \cdot e^{-K_{el} \cdot t_1}]$$

where C_t is the adjusted concentration at time t , $C_{t \text{ unadjusted}}$ is the observed concentration at time t , C_0 is the pre-product use concentration (-5 minutes), $K_{el} \frac{\ln(2)}{t_{1/2}}$, $t_{1/2}$ is 2 hours (average nicotine half-life), t is the actual sampling time since product administration, and t_1 is the actual sampling time since the time of the pre-product use sample. Any resulting negative concentration values following the baseline adjustment will be set to 0.

Nicotine PK parameters will be determined from the adjusted individual subject plasma concentration-time profiles by applying a non-compartmental approach using appropriate validated PK software (e.g., Phoenix[®] WinNonlin[®] version 8.1 or higher).

For each morning product use session on Days 1, through 5, the following PK parameters will be calculated from the baseline-adjusted nicotine concentration-time data:

- | | |
|----------------------|--|
| AUC ₀₋₉₀ | Area under the baseline-adjusted nicotine concentration-time curve from time 0 (defined as the start of the product use session) to the 90-minute time point as calculated by the linear trapezoidal method |
| AUC ₀₋₂₄₀ | Area under the baseline-adjusted nicotine concentration-time curve from time 0 (defined as the start of the product use session) to the 240-minute time point as calculated by the linear trapezoidal method |

| | |
|--------------------|---|
| AUC _t | Area under the baseline-adjusted nicotine concentration-time curve from time 0 (defined as the start of the product use session) to time t. |
| AUC _{inf} | Area under the baseline-adjusted nicotine concentration-time curve from time 0 (defined as the start of the product use session) extrapolated to infinity (represents the total nicotine exposure across time). |
| C _{max} | Maximum baseline-adjusted plasma concentration. |
| C _{last} | Plasma baseline-adjusted nicotine concentration at last time point measured |
| T _{max} | Time to reach the maximum baseline-adjusted plasma concentration. If the maximum value occurs at more than one time point, T _{max} is defined as the first time point with this value. |
| T _{1/2} | Terminal elimination half-life. |

Plasma concentrations below the limit of quantitation will be set to one-half of the lower limit of quantitation for the calculation of descriptive statistics of unadjusted plasma nicotine concentrations and for the calculation of baseline-adjusted nicotine concentrations.

Nicotine concentrations and PK parameters will be listed by subject and summarised by study product, by sex and overall using descriptive statistics.

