#### 8.3 Pharmacokinetic Concentrations

For the concentration tables, unadjusted plasma nicotine concentrations that are below the limit of quantification (BLQ) will be set to one-half of the lower limit of quantitation for the calculation of descriptive statistics.

Individual nicotine concentrations will be adjusted for baseline nicotine ("baseline-adjusted") and all PK parameters will be calculated based on the adjusted concentrations. Baseline adjustment will be performed by subtraction of the pre-existing nicotine concentration from

each nicotine concentration obtained after test product administration in that period/day for each subject using the following equation:

 $C_t = C_t \text{ unadjusted} - [C_0 \cdot e^{-Kel \cdot t1}]$ 

where Ct is the adjusted concentration at time t, Ct unadjusted is the observed concentration at time t, C0 is the pre-product use concentration (-5 minutes),  $K_{el} = \frac{\ln(2)}{T^{1/2}}$ , T1/2 is 2 hours (average nicotine half-life), t is the actual sampling time since product administration, and t1 is the actual sampling time since the time of the pre-product use sample.

After correction for pre-product administration values, some concentrations may be BLQ and some may be negative values. Negative values will be assigned a value of zero in the analyses and all other values obtained will be reported as is even if these values are BLQ.

Baseline-adjusted plasma nicotine concentrations will be used for the calculation of the plasma nicotine PK parameters.

All concentration data will be included in the calculation of the individual PK parameters, the individual concentration-time plots (based on actual sample times), and in the mean concentration-time plots (based on nominal sample times). However, if there are any significant deviations from nominal sample times, some concentration data may be excluded from the descriptive statistics and the mean concentration-time plots and/or additional concentration-time plots of the mean data may be provided. All deviations and excluded data will be listed and discussed in the CSR.

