# Table 8.1. Noncompartmental Pharmacokinetic Parameters to be Calculated

Parameter	Label to be Used in the Text, Tables and Figures	Definition	Method of Determination
AUC %extrap	AUC%extrap	Percent of AUC inf extrapolated to infinity	Calculated as: (1 – AUCt/AUCinf) x 100
C max	Cmax	Maximum baseline-adjusted plasma concentration over the duration of the measurement interval.	Taken from bioanalytical data adjusted for baseline
C last	Clast	Plasma baseline-adjusted nicotine concentration at last time point measured.	Taken from bioanalytical data adjusted for baseline
T max	T max	Time to reach the maximum baseline-adjusted plasma concentration. If the maximum value occurs at more than one time point, $T_{max}$ is defined as the first time point with this value	Taken from clinical database as the difference in the time of administration and the time of the blood draw which is associated with the $C_{max}$
T  / 2	T  / 2	Apparent first-order terminal elimination half-life.	Calculated as ln2/K el
K el	Kel	Apparent first-order terminal elimination rate constant	Calculated by linear least-squares regression analysis using the maximum number of points in the terminal log-linear period (e.g., three or more non-zero plasma concentrations).

Pharmacokinetic parameters will not be calculated for subjects with less than 3 consecutive post-product administration time points with quantifiable concentrations. Subjects for whom there are insufficient data to calculate the PK parameters will be included in the concentration tables only and excluded from the summary statistics, statistical analysis, and mean profiles.

The Kel will be determined using linear regressions composed of least 3 data points. The Kel will not be calculated if 1) the terminal elimination phase is not apparent, 2) if Cmax is one of the 3 last data points, or 3) if the R^2 value is less than 0.75. In cases where the Kel interval is not calculated, the values of T/2, AUCinf, and AUC%extrap will not be reported.

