## Note: Plasma Nicotine Concentration Tables (CPCONC1) will have the following format:

Page 1 of X

Unadjusted Plasma Nicotine Concentrations (ng/mL) Following Controlled Product Use of iD Balanced Blue Stick (Outcomes Population)

Subject Number	Product Sequence	Study Period	Sex	Pre-use	XX	XX	Samp XX	ole Times XX	(minutes) XX	XX	XX	XX	XX	XX
XX XX XX XX	XXXXXX XXXXXX XXXXXX	X X X	XX XX XX	XX XX XX XX	XX XX XX	XX XX XX	XX XX XX XX	XX XX XX	XX XX XX	XX XX XX	XX XX XX	XX XX XX	XX XX XX	XX XX XX
n Mean SD CV(%) SEM Minimum Median Maximum			Male**	X X.X X.XX XX.X XX.X X.XX XX XX XX	X X.X X.XX XX.X XX.X X.XX XX X.X XX XX	X X.X X.XX XX.X XX.X X.XX XX X.X X.X XX	X X.X X.XX XX.X X.XX X.XX XX X.X XX	X X.X X.XX XX.X XX.X XX XX XX XX XX	X X.X X.XX XX.X XX.X XX XX X.X XX XX	X X.X X.XX XX.X XX.X XX XX XX XX XX XX	X X.X X.XX XX.X XX.X X.XX XX X.X XX XX	X X.X X.XX XX.X XX.X X.XX XX X.X XX XX	X X.X X.XX XX.X XX.X X.XX XX X.X XX X.X	X X.X X.XX XX.X XX.X XX X.XX XX XX XX

Program: /CAXXXX/sas prg/pksas/PROGRAMNAME.SAS DDMMMYYYY HH:MM

Programming Notes: Footnotes to include under the table, as appropriate:

<. = Concentration value missing or not reportable.>

The following footnote will only be included in the unadjusted plasma nicotine tables: < For the calculation of summary statistics, values that are below the limit of quantitation (BLQ) of <XX> are treated as 1/2 LLQQ.>

\*\*There will also be summary statistics for female and overall

The following footnote will only be included in the baseline-adjusted plasma nicotine tables: < Prior to baseline adjustment, concentration values that are below the limit of quantitation (BLQ) of <XX> were set to 1/2 the LLQQ. After baseline adjustment, any negative values were assigned a value of zero and all other values obtained were reported as is (even if lower than the original limit of quantitation of <xx> ng/mL) for the calculation of the descriptive statistics.> For baseline-adjusted table, Pre-use will be replaced with 0.

Concentrations will be presented to same precision as in bioanalytical data.

Summary statistics presentation with respect to the precision of the bioanalytical data: n = integer; Mean and Median +1; SD and SEM +2, Min and Max +0, CV% to 1 decimal.

PK Time points are: pre-use and 2, 4, 6, 8, 10, 15, 30, 45, 60, 120 and 240 minutes following the start of product use.

Program:	/CAXXXXX/sas_prg/pksas/pk-conc-tables.sas	DDMMYYYY	HH:MM
Program:	/CAXXXXX/sas_prg/pksas/pk-conc-tables-sig.sas	DDMMYYYY	HH:MM

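### Half-LLOQ imputed late samples can enter the Kel regression and serve as Clast, so T1/2 and AUCinf can be biased, usually downward, when the 240-minute sample is below the assay limit

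*Protocol*

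**What the plan says.** The rule is spread over four places.

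- **Protocol 7.3.1** sets samples below the limit of quantitation (BLQ) to half the lower limit (LLOQ): "Plasma concentrations below the limit of quantitation will be set to one-half of the lower limit of quantitation for the calculation of descriptive statistics". That clause concerns the raw values; the same sentence then extends the substitution to the adjusted ones, "and for the calculation of baseline-adjusted nicotine concentrations". The concentration-table shell CPConc1 in SAP 15.2 repeats the order: "Prior to baseline adjustment, concentration values that are below the limit of quantitation (BLQ) of <XX> were set to 1/2 the LLQQ" (LLQQ is the shell's spelling).
- **SAP 8.3** sets negative adjusted values to zero; "all other values obtained will be reported as is even if these values are BLQ". It adds: "All concentration data will be included in the calculation of the individual PK parameters".
- **SAP Table 8.1** fits Kel by regression "using the maximum number of points in the terminal log-linear period (e.g., three or more non-zero plasma concentrations". Clast is the adjusted value at the last time measured, and AUCinf is AUCt plus Clast/Kel.
- **SAP 8.4** has guards. No PK parameter is calculated without three consecutive quantifiable post-use samples. Kel is withheld if the terminal phase is not apparent, if Cmax is among the last three points, or if R² is below 0.75. T1/2, AUCinf and AUC%extrap are then not reported.

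**The concern.** The profile-level guard speaks of quantifiable concentrations, but the Kel row asks only for non-zero ones. An imputed value that stays positive after adjustment passes the weaker test. Only the 120- and 240-minute samples follow the 60-minute one, so a single imputed value at 240 minutes can largely set the slope and also be Clast.

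Weaker-delivery sessions lose the late sample to the LLOQ more often than cigarette sessions do. T1/2 and AUCinf serve secondary objective 1 and are tabulated by product. A shorter half-life for a weaker product in the same subjects could be read as a property of the product when it comes from the imputation. This does not depend on the fixed 2-hour half-life being wrong for anyone: it arises when every true half-life is exactly 2 hours.

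**Working it through.** The plan states no figure to reproduce. The LLOQ is a placeholder in the shell, so results are in multiples of L = LLOQ.

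**From the documents:** sampling at −5 (pre-use), 2, 4, 6, 8, 10, 15, 30, 45, 60, 120 and 240 min; BLQ = L/2; adjusted C = observed − C0·exp(−ln2·t1/120), with t1 = t + 5; negatives set to 0; linear trapezoid.

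**Assumed:** linear rise to a peak increment P at 8 min; terminal half-life 120 min; C0 and P as given below.

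**1. Does the imputed value stay positive?** At 240 min the decay factor is exp(−ln2·245/120) = 0.243, so L/2 survives adjustment while C0 < 0.5/0.243 = 2.06L. If C0 is itself BLQ, the result is 0.5L·(1 − 0.243) = 0.379L, whatever the true level.

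**2. When is 240 min BLQ?** With no baseline and no fast distribution phase, when P·exp(−ln2·232/120) < L, that is P < 3.8L. For the 120-min sample the threshold is P < 1.9L. A fast phase raises both.

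**3. Worked case: C0 = 0.5L, P = 3L, one exponential.** C0 is BLQ and is set to exactly its true value, which isolates the post-use imputation.

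| Minutes | 60 | 120 | 240 |
|---|---|---|---|
| True increment (L) | 2.222 | 1.571 | 0.785 |
| Observed (L) | 2.565 | 1.814 | 0.907 (BLQ) |
| Adjusted as written (L) | 2.222 | 1.571 | 0.379 |

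- Logs of the adjusted values: 0.798, 0.452, −0.971. Time deviations from 140: −80, −20, 100; sum of squares 16,800.
- Slope = (−80·0.798 − 20·0.452 − 100·0.971)/16,800 = −0.01012 per min, so T1/2 = 0.693/0.01012 = 68 min, with R² = 0.98.
- AUCinf as written = 377.6 + 0.379/0.01012 = 415. From the full profile it is 402.0 + 0.785/0.005776 = 538. The written rule is 23% low.
- A fit from 30 to 240 min gives T1/2 75 min and AUCinf 418 (22% low).

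**4. Other one-exponential cases, fit window chosen by adjusted R²:**

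| C0 | P | T1/2 (true 120) | AUCinf, written vs full |
|---|---|---|---|
| 0.5L | 1.5L | 117 | 263 vs 269 (−2%) |
| 0.5L | 2L | 97 | 312 vs 359 (−13%) |
| 2L | 1.5L | 30 | 179 vs 269 (−33%) |

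R² was 0.92 or higher, so the 0.75 limit did not act.

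**5. Both late samples BLQ.** With C0 also BLQ, the adjusted values are 0.257L at 120 min and 0.379L at 240 min: they rise. Kel was not calculable under the written guards in any noise-free case of this kind, so T1/2 and AUCinf are missing there.

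**6. Frequency.** Assumed: Cmax 4 and LLOQ 0.5 ng/mL, fast half-life 10 min, between-profile log-SD 40%, C0 0.16 to 0.47 ng/mL, assay CV 7%. The 240-min sample is BLQ in 1% of profiles with no fast phase, 17% with a 40% fast phase and 53% with 60%. A repeat gave 50% for the last, so about 1% to 50%. Across settings, median T1/2 in profiles with a BLQ 240-min sample was about 54 to 91 min, against about 115 to 122 when it was quantifiable.

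**7. Effect of excluding raw-BLQ samples.** In the case of step 3, fitting 45, 60 and 120 min gives T1/2 = 120, and AUCinf = 260.6 + 1.571/0.005776 = 533 (1% low). In Monte Carlo settings exclusion moved median T1/2 from 72 to 116, 70 to 106 and 73 to 93 min. With a 60% fast phase and the weakest products it made matters worse (91 to 72, 89 to 56), because slopes were fitted to early points. A noise-free 70% fast-phase case shows why: at C0 = 0.5L and P = 4L both late samples are BLQ, the written rule withholds Kel, and exclusion alone reports 38 min against 112 from the full profile.

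**The case against.** Several points on the other side stand.

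- A reader might infer that T1/2 and AUCinf are simply wrong under this plan. The documents do not support that. Bias needs a BLQ 240-minute sample, and no LLOQ, expected Cmax or C0 is given. At P = 20L no late sample is BLQ and the rule has no effect.
- A reader might take the rise from 0.257L to 0.379L as the main harm. It needs both late samples BLQ, which is where the existing guards often withhold Kel. The damaging pattern is a BLQ value at 240 minutes alone.
- No product is described as low-delivery; the protocol says only that the heated herbal aerosol contains nicotine. The direction (weaker delivery, more BLQ samples) holds, but no product can be named.
- Whole-product medians move less than the BLQ subset. With a 40% fast phase, Cmax 4 and LLOQ 0.5, they were 114 to 115 min as written and 115 to 117 after exclusion.
- Kel intervals, R² and number of points are listed by subject, and BLQ values are marked in the concentration tables, so affected profiles can be traced.
- Exclusion alone can report slopes from the distribution phase that the present rules withhold.

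These limit the size of the problem and shape the remedy. They do not supply the missing rule: no sentence says whether an imputed sample may enter Kel or serve as Clast.

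**Conclusion.** The concern holds in conditional form. As written, an imputed 240-minute value may set both the slope and Clast. When that sample is BLQ and the 120-minute sample is not, T1/2 and AUCinf can be biased, usually downward and usually unflagged by R². In the noise-free cases AUCinf was 2% to 33% low; with a 50% fast phase, C0 = 1L and P = 2L the effect was negligible (T1/2 114 against 117, AUCinf 1% low). These sizes rest on the assumed profiles, and the 1% to 50% frequency on an assumed LLOQ, Cmax and fast-phase fraction.

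It would go too far to infer that the primary comparison is compromised. T1/2 and AUCinf are summarised descriptively and do not enter the mixed model. Late-sample imputation does not reach Cmax. AUCt moves much less than AUCinf: in the worked case 377.6 against 402.0, or 6% low. The point is worth a wording change because the bias differs by delivery level and could pass for a product difference.

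**What to change.** In the SAP Table 8.1 Kel row, replace the non-zero criterion with: three or more samples whose observed (unadjusted) concentration is at or above the LLOQ and whose adjusted value is above zero. Then:

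- Require these points to include the 120-minute or a later sample. This withholds the 38-minute result in step 7.
- Apply the existing guards (terminal phase apparent, Cmax not among the last three points, R² at least 0.75) to the remaining points. Otherwise do not report Kel, T1/2, AUCinf or AUC%extrap.
- For AUCinf and AUC%extrap only, use Clast and the AUC up to the last such sample. Leave the reported primary AUCt unchanged; cutting it at the last quantifiable sample would shorten it (at C0 = 0.5L and P = 1.5L, 130 against 199 as written and 201 for the full profile).
- Report BLQ samples by product and time point, and sessions with T1/2 not reported by product.

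The cost is SAP wording and two counts. T1/2 and AUCinf will be missing for some low-delivery sessions. Some downward bias remains if a fast phase extends into the fitted points: with a 70% fast phase and C0 = 0.5L, exclusion gives 86 min where the full profile gives 112, against 75 as written at P = 8L but 93 at P = 6L.
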